10.6.3. Dose Level Review Committee

A Dose Level Review Committee will evaluate safety data following the completion of each dose observation period of the Phase 1b portion. The same committee will review safety data in the event that an interim analysis for Phase 2 will be performed. Members of this committee will include the Sponsor (at a minimum: the Medical Monitor or designee, a Drug Safety representative and a Biostatistician) as well as participating Investigators/designees.

11. ADVERSE EVENT REPORTING

Timely, accurate, and complete reporting and analysis of safety information from clinical studies are crucial for the protection of subjects, Investigators, and the Sponsor, and are mandated by regulatory agencies worldwide. The Sponsor has established Standard Operating Procedures in conformity with regulatory requirements worldwide to ensure appropriate reporting of safety information; all clinical studies conducted by the Sponsor or its affiliates will be conducted in accordance with those procedures.

11.1. Adverse Event Definitions and Classifications

11.1.1. Adverse Events

An AE is any untoward medical occurrence in a patient administered a pharmaceutical product and which does not necessarily have a causal relationship with this treatment. An AE can therefore be any unfavorable and unintended sign (including a clinically significant abnormal laboratory finding, for example), symptom, or disease temporally associated with the use of an investigational study drug, whether or not considered related to the study drug ([ICH-E2A 1995](#)).

For the purposes of this clinical study, AEs include events which are either new or represent detectable exacerbations of pre-existing conditions.

Disease progression is not an adverse event; rather it may be the cause of an adverse event. The clinical diagnosis that is associated with disease progression must be reported as all other adverse events. “Disease progression” should never be used as an adverse event term.

Adverse events may include, but are not limited to:

- Subjective or objective symptoms spontaneously offered by the subject and/or observed by the Investigator or study staff including laboratory abnormalities of clinical significance.
- Any AEs experienced by the subject through the completion of final study procedures.
- AEs not previously observed in the subject that emerge during the protocol-specified AE reporting period, including signs or symptoms associated with DLBCL that were not present before the AE reporting period
- Complications that occur as a result of protocol-mandated interventions (eg, invasive procedures such as biopsies).

The following are NOT considered AEs:

- **Pre-existing condition:** A pre-existing condition (documented on the medical history eCRF) is not considered an AE unless the severity, frequency, or character of the event worsens during the study period.
- **Pre-planned or elective hospitalization:** A hospitalization planned before signing the informed consent form is not considered an SAE, but rather a therapeutic intervention. However, if during the pre-planned hospitalization an event occurs, which prolongs the hospitalization or meets any other SAE criteria, the event will be considered an SAE. Surgeries or interventions that were under consideration, but not performed before enrollment in the study, will not be considered serious if they are performed after enrollment in the study for a condition that has not changed from its baseline level. Elective hospitalizations for social reasons, solely for the administration of chemotherapy, or due to long travel distances are also not SAEs.
- **Diagnostic Testing and Procedures:** Testing and procedures should not to be reported as AEs or SAEs, but rather the cause for the test or procedure should be reported.
- **Asymptomatic Treatment Related Lymphocytosis:** This event should not be considered an AE. Patients with treatment-related lymphocytosis should remain on study treatment and continue with all study-related procedures.

11.1.2. Serious Adverse Events

A serious adverse event based on ICH and EU Guidelines on Pharmacovigilance for Medicinal Products for Human Use is any untoward medical occurrence that at any dose:

- Results in death (ie, the AE actually causes or leads to death).

- Is life-threatening. Life-threatening is defined as an AE in which the patient was at risk of death at the time of the event. It does not refer to an event which hypothetically might have caused death if it were more severe. If either the Investigator or the Sponsor believes that an AE meets the definition of life-threatening, it will be considered life-threatening.
- Requires in-patient hospitalization >24 hours or prolongation of existing hospitalization.
- Results in persistent or significant disability/incapacity (ie, the AE results in substantial disruption of the patient's ability to conduct normal life functions).
- Is a congenital anomaly/birth defect.
- Is an important medical event that may not result in death, be immediately life-threatening or require hospitalization, but may be considered an SAE when, based upon appropriate medical judgment, the event may jeopardize the patient or patient may require intervention to prevent one of the other outcomes listed in this definition. Examples of such events are intensive treatment in an emergency department or at home for allergic bronchospasm, blood dyscrasias, or convulsion that does not result in hospitalization; or development of drug dependency or drug abuse.

Given that the Investigator's perspective may be informed by having actually observed the event, and the Sponsor is likely to have broader knowledge of the drug and its effects to inform its evaluation of the significance of the event, if either the Sponsor or the Investigator believes that the event is serious, the event will be considered serious.

11.1.3. Unexpected Adverse Events

An "unexpected" AE is an AE that is not listed in the Investigator's Brochure/package insert or is not listed at the specificity or severity that has been observed. For example, hepatic necrosis would be "unexpected" (by virtue of greater severity) if the Investigator's Brochure referred only to elevated hepatic enzymes or hepatitis. Similarly, cerebral thromboembolism and cerebral vasculitis would be "unexpected" (by virtue of greater specificity) if the Investigator's Brochure/package insert listed only cerebral vascular accidents. "Unexpected" also refers to AEs that are mentioned in the Investigator's Brochure as occurring with a class of drugs or as anticipated from the pharmacological properties of the drug, but are not specifically mentioned as occurring with the study drug under investigation.

11.1.4. Severity Criteria (Grade 1-5)

Definitions found in the Common Terminology Criteria for Adverse Events version 4.03 ([CTCAE v4.03](#)) will be used for grading the severity (intensity) AEs. The [CTCAE v4.03](#) displays Grades 1 through 5 with unique clinical descriptions of severity for each referenced AE. Should a subject experience any AE not listed in the [CTCAE v4.03](#), the following grading system should be used to assess severity:

- Grade 1 (Mild AE) – experiences which are usually transient, requiring no special treatment, and not interfering with the subject's daily activities

- Grade 2 (Moderate AE) – experiences which introduce some level of inconvenience or concern to the subject, and which may interfere with daily activities, but are usually ameliorated by simple therapeutic measures
- Grade 3 (Severe AE) – experiences which are unacceptable or intolerable, significantly interrupt the subject's usual daily activity, and require systemic drug therapy or other treatment
- Grade 4 (Life-threatening or disabling AE) – experiences which cause the subject to be in imminent danger of death
- Grade 5 (Death related to AE) – experiences which result in subject death

11.1.5. Causality (Attribution)

The Investigator is to assess the causal relation (ie, whether there is a reasonable possibility that the study drug caused the event) using the following definitions:

Not Related:	Another cause of the AE is more plausible; a temporal sequence cannot be established with the onset of the AE and administration of the investigational product; or, a causal relationship is considered biologically implausible.
Unlikely:	The current knowledge or information about the AE indicates that a relationship to the investigational product is unlikely.
Possibly Related:	There is a clinically plausible time sequence between onset of the AE and administration of the investigational product, but the AE could also be attributed to concurrent or underlying disease, or the use of other drugs or procedures. Possibly related should be used when the investigational product is one of several biologically plausible AE causes.
Related:	The AE is clearly related to use of the investigational product.

11.2. Documenting and Reporting of Adverse Events

The Investigator is responsible for ensuring that all AEs and SAEs observed or reported during the study, as outlined in the prior sections, are recorded on the eCRF. All SAEs must also be reported on the Serious Adverse Event Report Form and submitted to the Sponsor (see [Section 11.2.2.2](#)).

11.2.1. Special Reporting Situations

Safety events of interest on a Sponsor study drug that may require expedited reporting and/or safety evaluation include, but are not limited to:

- Overdose of a study drug
- Suspected abuse/misuse of a study drug

- Inadvertent or accidental exposure to a study drug
- Medication error involving a product (with or without subject/patient exposure to the study drug, eg, name confusion)

Special reporting situations should be recorded in the eCRF. Any special reporting situation that meets the criteria of a SAE should be recorded on the AE eCRF.

11.2.2. Adverse Event Reporting Procedures

11.2.2.1. All Adverse Events

All subjects who receive at least one dose of study drug(s) will be considered evaluable for safety assessments. All AEs whether serious or non-serious, will be recorded in the source documents from the time signed and dated ICF is obtained until 30 days following the last dose of study drug. Starting from the time of first dose of study drug, all AEs and SAEs will be entered in the eCRF until 30 days after the date of last dose of study drug. Serious Adverse Events that occur during study conduct including the screening period must be reported to the Sponsor. Serious adverse events occurring more than 30 days following the last dose of study drug should also be reported if considered related to any of the study drugs. Resolution information after 30 days should be provided.

Progressive disease should NOT be reported as an AE, but instead symptoms/clinical signs of disease progression may be reported. Otherwise, all events that meet the definition of a SAE will be reported as SAEs, regardless of whether they are protocol-specific assessments.

All AEs, regardless of seriousness, severity, or presumed relationship to study drug, must be recorded using medical terminology in the source document. All records will need to capture the details of the duration and the severity of each episode, the action taken with respect to the study drug, Investigator's evaluation of its relationship to the study drug, and the event outcome. Whenever possible, diagnoses should be given when signs and symptoms are due to a common etiology (eg, cough, runny nose, sneezing, sore throat, and head congestion should be reported as "upper respiratory infection"). Investigators must record in the eCRF their opinion concerning the relationship of the adverse event to study therapy. All measures required for adverse event management must be recorded in the source document and reported according to Sponsor instructions.

11.2.2.2. Reporting Criteria for Serious Adverse Events

All SAEs occurring during the study must be reported to the Sponsor by the study-site within 24 hours of their knowledge of the event.

Information regarding SAEs will be transmitted to Pharmacyclics using the Serious Adverse Event Report Form, which must be completed by a study physician from the study site, and submitted to Pharmacyclics within 24 hours of the study site becoming aware of the event.

All SAEs that have not resolved by the end of the study, or that have not resolved upon discontinuation of the subject's participation in the study, must be followed until any of the following occurs:

- The event resolves
- The event stabilizes
- The event returns to baseline, if a baseline value/status is available
- The event can be attributed to agents other than the study drug or to factors unrelated to study conduct
- It becomes unlikely that any additional information can be obtained (subject or health care practitioner refusal to provide additional information, lost to follow up after demonstration of due diligence with follow-up efforts)

11.2.3. Events of Special Interest

Specific AEs or groups of AEs will be followed as part of standard safety monitoring activities by the Sponsor. These events will be reported to Pharmacyclics within 24 hours of awareness irrespective of seriousness (ie, serious and non-serious adverse events) following the procedure described above for SAEs and will require enhanced data collection.

11.2.3.1. Major Hemorrhage

Major hemorrhage is defined as any of the following:

1. Any treatment-emergent hemorrhagic adverse events of Grade 3 or higher*.
2. Any treatment-emergent serious adverse events of bleeding of any grade
3. Any treatment-emergent central nervous system hemorrhage/hematoma of any grade

*All hemorrhagic events requiring transfusion of red blood cells should be reported as grade 3 or higher AE per [CTCAE, v4.03](#).

Events meeting the definition of major hemorrhage will be captured as an event of special interest according to [Section 11.2.3](#) above.

11.2.4. Other Malignancies

All new malignant tumors including solid tumors, skin malignancies and hematologic malignancies will be reported as SAEs. This includes any second primary malignancy, regardless of causal relationship to study drug[s], occurring at any time for the duration of the study, from the time of signing the informed consent to 3 years after the last study drug treatment.

Events of second primary malignancy are to be reported using the SAE form; these events must also be documented in the appropriate page(s) of the eCRF and in the subject's source documents. Documentation of the diagnosis of the second primary malignancy must be provided

at the time of reporting as an SAE (eg, any confirmatory histology or cytology results, X-rays, CT scans, etc.).

11.2.5. Pregnancy

Before study enrollment, subjects must agree to take appropriate measures to avoid pregnancy. However, should a pregnancy occur in a female study subject, consent to provide follow-up information regarding the outcome of the pregnancy and the health of the infant (until 30 days old) will be requested.

A female subject must immediately inform the Investigator if she becomes pregnant from the time of consent to 30 days after the last dose of study drug. A male subject must immediately inform the Investigator if his partner becomes pregnant from the time of his consent to 90 days after the last dose of study drug. Any female subjects receiving study drug(s) who become pregnant must immediately discontinue study treatment. The Investigator should counsel the subject, discussing any risks of continuing the pregnancy and any possible effects on the fetus.

11.2.5.1. Pregnancy Reporting

Although pregnancy itself is not regarded as an adverse event, the outcome will need to be documented. Any pregnancy occurring in a subject or subject's partner from the time of consent to 30 days after the last dose of study drug must be reported. Any occurrence of pregnancy must be recorded on the Pregnancy Report Form Part I and submitted to Pharmacyclics Drug Safety, or designee, within 24 hours of learning of the event. All pregnancies will be followed for outcome, which is defined as elective termination of the pregnancy, miscarriage, or delivery of the fetus. For pregnancies with an outcome of live birth, the newborn infant will be followed until 30 days old by completing the Pregnancy Report Form Part II. Any congenital anomaly/birth defect noted in the infant must be reported as a serious adverse event.

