1.9. Summary of Clinical Safety for Lenalidomide in Lymphoma

Lenalidomide is currently approved for the treatment of relapsed or refractory mantle cell lymphoma at a recommended starting dose of 25 mg orally once daily for 21 days every 28 days.

The safety data for 134 patients receiving monotherapy for MCL has been evaluated. The most common treatment-emergent adverse events (>15%) were neutropenia (49%), thrombocytopenia (36%), fatigue (34%), diarrhea (31%), anemia (31%), nausea (30%), cough (28%), pyrexia (23%), rash (22%), dyspnea (18%), pruritis (17%), constipation (16%), and peripheral edema (16%). The most common Grade 3 or 4 adverse events were hematologic in nature: neutropenia (43%), thrombocytopenia (28%), and anemia (11%). Pneumonia (9%) was the most frequent non-hematologic Grade 3/4 adverse event.

The median duration of treatment in this patient population was 95 days (1-1002 days). Seventy-six patients (57%) required at least one dose interruption for an adverse event, while 51 patients (38%) had at least one dose reduction due to toxicity. Twenty-six patients (19%) discontinued treatment due to adverse events.

Lenalidomide has a black box warning for embryo-fetal toxicity, hematologic toxicity and venous thromboembolism.

Complete and updated safety information is available in the current [Revlimid® Investigator's Brochure](#).

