17. Female subjects of child bearing potential (FCBP)^b and male subjects who are sexually active must use TWO acceptable methods of birth control, one highly effective method of birth control plus one additional effective method of birth control for at least 28 days prior to study treatment and during the study treatment period. For female subjects, these birth control requirements must be adhered to for 12 months after the last dose of rituximab or 30 days after the last dose of ibrutinib and lenalidomide, whichever is later. For male subjects, these birth control requirements must be adhered to for 90 days after the last dose of ibrutinib and lenalidomide, whichever is later. Male subjects must agree to not donate sperm during the study treatment period and up to 90 days after the last dose of ibrutinib and lenalidomide.
18. Life expectancy of more than 3 months.

^b A female of childbearing potential (FCBP) is a sexually mature female who: 1) has not undergone a hysterectomy or bilateral oophorectomy; or 2) has not been naturally postmenopausal for at least 24 consecutive months (ie, has had menses at any time in the preceding 24 consecutive months).

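### Partner pregnancies on days 31-90 after the last dose must be told to the Investigator but fall outside the protocol's explicit window for reporting to the sponsor

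*Protocol*

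**What the plan says.** Two adjacent parts of the protocol deal with pregnancy.

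- **Section 11.2.5 (telling the Investigator).** A female subject must do so "if she becomes pregnant from the time of consent to 30 days after the last dose of study drug". A male subject must do so "if his partner becomes pregnant from the time of his consent to 90 days after the last dose of study drug".
- **Section 11.2.5.1 (reporting onward).** One window covers both sexes. The sentence names the partner as well as the subject, and a pregnancy in either "from the time of consent to 30 days after the last dose of study drug must be reported". The next sentence gives the mechanism: "Any occurrence of pregnancy must be recorded on the Pregnancy Report Form Part I and submitted to Pharmacyclics Drug Safety", or a designee, within 24 hours of learning of it. The section then requires pregnancies to be followed to outcome and live-born infants to 30 days of age. Any congenital anomaly must be reported as an SAE.

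For men, inclusion criterion 17 in Section 4.1 says that "these birth control requirements must be adhered to for 90 days after the last dose of ibrutinib and lenalidomide". The SAP does not mention pregnancy reporting.

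**The concern.** The 90-day period for partners in Section 11.2.5 is not carried into the section that moves the information from site to sponsor. An Investigator who learns of a partner pregnancy arising on, say, day 60 holds information that the protocol required the subject to disclose. The sentence that says which pregnancies must be reported stops at day 30.

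The protocol gives its own reasons for wanting these reports. Section 1.9 states: "Lenalidomide has a black box warning for embryo-fetal toxicity". Appendix 8 says that lenalidomide has been found in semen. Section 1.5.2 records malformations with ibrutinib in rats and rabbits. At stake is how completely pregnancies with possible paternal drug exposure are recorded, including those that end in miscarriage, termination or a normal birth.

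**Working it through.** There is no sample size, error rate or event count to reproduce. The check sets the windows side by side.

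| Pregnancy in | Tell the Investigator (11.2.5) | Report onward (11.2.5.1) | Difference |
|---|---|---|---|
| Female subject | last dose + 30 days | last dose + 30 days | 30 - 30 = 0 days |
| Partner of male subject | last dose + 90 days | last dose + 30 days | 90 - 30 = 60 days (days 31-90) |

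1. **Are the windows comparable?** Yes. Both start at consent, both count from the last dose of study drug, and both depend on when the pregnancy arises rather than when it is discovered.
2. **Could the 30-day limit be meant for female subjects only?** No. The sentence in Section 11.2.5.1 names the subject's partner.
3. **Is 90 days a stray figure?** No. It is also the period for male contraception and sperm donation in Section 4.1, criterion 17. The same period applies to condom use and semen donation by men after lenalidomide in Appendix 7 and in Appendix 8, Sections 2.3.2 and 2.5.2.2. The 30-day limit for partners is the odd one out, and it equals the limit for female subjects.
4. **Does anything else in Section 11.2.5.1 cover days 31-90?** Possibly. The sentences on the report form and on follow-up have no time limit. Read alone, they reach any pregnancy the site learns of. Read in sequence, they describe how to handle the pregnancies just defined. The second reading is more natural, but the text does not settle it.
5. **Does the SAE route cover days 31-90?** In part. Section 11.1.2 lists a congenital anomaly as an SAE criterion, Section 11.2.5.1 requires one to be reported as an SAE, and Section 11.2.2.1 extends SAE reporting beyond 30 days when the event is considered related to a study drug. But Section 11.2.5.1 also says that pregnancy itself is not regarded as an adverse event. This route therefore secures neither the initial report nor prospective follow-up, and it depends on the site learning the outcome.

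**The case against.** The strongest reply is that the protocol does not say these pregnancies may go unreported. The sentences on the form and on follow-up are unrestricted. A careful site told of a day-60 partner pregnancy could submit the form within 24 hours and believe that it had followed the text. A birth defect, the gravest outcome, has its own written route. Numbers are also likely to be small: men must use condoms for at least 90 days even after vasectomy (Appendices 7 and 8), and Section 1.2 gives a median age at diagnosis of 67 years.

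Most of this stands, and it limits the point. It does not remove it, because two sites could handle the same pregnancy differently and both cite the protocol.

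Three stronger readings are tempting and are not supported:

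- **That pregnancies on days 31-90 need not be reported or followed, so that fetal outcomes would be lost.** This holds only on the stricter reading of Section 11.2.5.1, and even then birth defects have the SAE route.
- **That the women's contraception period, "for 12 months after the last dose of rituximab or 30 days after the last dose of ibrutinib and lenalidomide, whichever is later", reveals a second gap.** It applies to female subjects, whose notification and reporting windows already agree at 30 days. A contraception period need not equal a reporting window.
- **That 60 of 90 days means two-thirds of the risk goes unrecorded.** That is a share of calendar days after treatment. It is not a share of exposure, risk or expected pregnancies, and it leaves out the on-treatment period, which is fully covered.

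**Conclusion.** The inconsistency is real and narrow. For partners of male subjects, the duty to tell the Investigator runs 60 days longer than the explicit duty to report onward. On days 31-90 the reporting duty is ambiguous, and the SAE rules fill the gap only for birth defects.

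This rests on reading the 30-day sentence as setting the scope of the sentences that follow it. If those are read as free-standing, reporting is already required and the fault is one of clarity alone. Either way the two sections need reconciling. The documents give no rate of partner pregnancy, so the number of affected reports cannot be estimated.

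The consequence is confined to the completeness and consistency of safety reporting. The primary endpoint, sample size, interim rule and SAP analyses are untouched. On the drug, the protocol's own language for humans is that a teratogenic effect cannot be ruled out (Appendices 7 and 8), alongside the boxed warning. The case for acting needs nothing stronger.

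**What to change.** Reconcile Section 11.2.5.1 with Section 11.2.5. State the reporting window separately for female subjects and for partners of male subjects, and make the partner window the same as the one for notifying the Investigator. Add that the form, the 24-hour submission to the sponsor and the follow-up to outcome apply to every pregnancy so notified, which removes the ambiguity left by the sentences without a time limit.

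The cost is about one sentence in the protocol and at most a few extra report forms. No dose, treatment schedule, contraception requirement or analysis changes, and the SAP needs no edit.
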